## **6.6 Dose modification**

Not applicable.

## **6.7 Treatment after the end of the study**

Not applicable.

# **7 DISCONTINUATION OF STUDY MEDICATION AND STUDY PARTICIPANT DISCONTINUATION/WITHDRAWAL**

## **7.1 Discontinuation of IMP**

Not applicable; eligible study participants are randomized to receive a single-dose administration of bimekizumab 320mg in UP0068.

### **7.1.1 Criteria for study hold due to adverse events**

During the study, planned dosing and procedures must be discontinued or suspended for all remaining study participants not yet dosed in the study and appropriate follow-up procedures established for (but not limited to) any of the following reasons:

- A pattern of AEs, considered as related to the study drug, occurs that in the opinion of the Investigator and/or UCB Study Physician contraindicates the further dosing of additional study participants.
- If the Sponsor or its designee judges it necessary for medical, safety, regulatory, or any other reasons consistent with applicable laws, regulations, and Good Clinical Practice (GCP).

Where it is possible to do so without threatening the safety of study participants, such discontinuation/suspension should be discussed with the UCB Study Physician prior to its implementation.

## **7.2 Study participant discontinuation/withdrawal from the study**

Study participants are free to withdraw from the study at any time, without prejudice to their continued care and without having to provide any reason.

A study participant may withdraw from the study at any time at his/her own request, or may be withdrawn at any time at the discretion of the Investigator for safety, behavioral, compliance, or administrative reasons.

If the study participant withdraws consent for disclosure of future information, the Sponsor may retain and continue to use any data collected before such a withdrawal of consent.

If a study participant withdraws from the study, he/she may request destruction of any samples taken and not tested, and the Investigator must document this in the site study records.

See the schedule of activities for data to be collected at the time of study discontinuation and follow-up and for any further evaluations that need to be completed.

Study participants should be discontinued from the study if any of the following events occur:

1. Study participant develops an illness that would interfere with his/her continued participation as per the Investigator's judgment.

---

2. Study participant is noncompliant with the study procedures in the opinion of the Investigator.
3. Study participant takes prohibited concomitant medications as defined in this protocol.
4. Study participant withdraws his/her consent.
5. There is confirmation of a pregnancy during the study, as evidenced by a positive pregnancy test.
6. The Sponsor or a regulatory agency requests withdrawal of the study participant.
7. Participation in any other study during the duration of this study.

Participants must be withdrawn by the Investigator based on discussion with the Sponsor under the following circumstances:

- Any confirmed COVID-19 case that warrants discontinuation in the judgment of the Investigator or Sponsor to protect the safety of the participant, other participants, or study site staff.

Investigators should contact the Medical Monitor, whenever possible, to discuss the withdrawal of a study participant in advance. Study participants will be encouraged to return for a Safety Follow-up Visit following premature discontinuation from the study.

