e Vital signs include BP, pulse rate, and tympanic body temperature. Body temperature only will be measured at outpatient visits without regular vital signs measurement (Days 4, 5, 6, 7, 8, 10, 13, 16, 19, 22, and 28).

f During the inhouse treatment period, vital signs and ECGs should be measured/taken prior to blood sampling, where applicable, with the study participant resting in the supine position for at least 3 minutes. Vital signs and ECGs will be measured on Day 1 at predose, at 1.5h, 5h, and 11h postdose, on Day 2 at 24h postdose, and on Day 3 at 48 hours postdose, then on Days 9, 25, 56, 84, 112, and 140.

g Height will be recorded only at the Screening Visit.

h As this is a single-dose study, device presentation deficiencies are only to be captured on Day 1 (ie, the day when IMP is administered during the inhouse treatment period).

i Serology variables include HbsAg, HBc-Ab, HCV-Ab (both IgG and IgM), HIV1-Ab, HIV1-Ag, and HIV-2 Ab.

j Blood sampling for hematology (including coagulation and hemostasis) and clinical chemistry will be performed at the Screening Visit, and Days -1, 2, 9, 25, 56, 84, 112, and the SFU Visit.

k Urinalysis via dipstick will be performed at Screening, Day-1, Days 2, 9, 25, 56, 84, 112, and 140.

l The PK sampling time points will be as follows: predose within 15 minutes at maximum before dosing, and 1.5h, 5h, 24h, 48h postdose, and from Day 4 onwards at every visit (ie, Days 4 to 10, 13, 16, 19, 22, 25, 28, 56, 84, 112, and 140).

m ADAb samples will be taken predose and on Days 13, 28, 56, 84, 112, and 140; blood samples will be processed as specified in the laboratory manual.

n Pregnancy tests will be performed at the Screening Visit, Day-1, Days 28, 56, 84, 112, and Day 140. Prior to dosing, the test should be performed in serum; post dosing the test may be performed in urine. The FSH test will be performed in postmenopausal women at the Screening Visit.

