##### **6.5.2 Prohibited concomitant treatments (medications and therapies)**

With the exception of those medications listed in Section 6.5.1 and medications necessary for the treatment of TEAEs per Investigator discretion, no prescription or nonprescription medicines are allowed within 30 days (or 5 half-lives of the respective medication, whichever is longer) prior to randomization and until the SFU Visit (Day 140).

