## **5.2 Protocol deviations**

IPDs will be identified and classified by the deviation types listed in the IPD specification document.

IPDs will be summarized by treatment group and overall using the RS. The summary will include the following:

- Number and percentage of participants with no IPDs
- Number and percentage of participants with at least one IPD
- Number and percentage of participants by type of protocol deviation

By-participant listings of IPDs as identified in the DEMs will be provided by treatment group using the RS. This will include deviation type, deviation description, and whether the deviation led to exclusion from the PK-PPS. Similar listings and tables will be produced for IPDs related to COVID-19.

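### After the single dose, the withdrawal rule for prohibited medication or noncompliance ends PK, ADAb and safety sampling before anyone has judged whether the deviation matters

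*Protocol*

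**What the plan says.** Protocol Section 7.1 treats discontinuation of study drug as having no meaning in this trial: "Not applicable; eligible study participants are randomized to receive a single-dose administration of bimekizumab 320mg in UP0068". Section 7.2 then sets a rule about leaving the study: "Study participants should be discontinued from the study if any of the following events occur". Item 2 of its list is "Study participant is noncompliant with the study procedures in the opinion of the Investigator". Item 3 is "Study participant takes prohibited concomitant medications as defined in this protocol". Neither item distinguishes before from after the Day 1 dose.

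The medication ban is in Protocol Section 6.5.2: "no prescription or nonprescription medicines are allowed within 30 days" (or five half-lives, if longer) before randomization, and it then runs to the Day 140 visit. It exempts the permitted list in Section 6.5.1 and medicines the Investigator considers necessary to treat treatment-emergent adverse events.

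PK samples are scheduled at every visit to Day 140 (Protocol Table 1-1). After premature discontinuation, Section 7.2 only encourages an SFU Visit. The SFU column of Table 1-1 includes one PK sample, and Section 8.10 asks for an ADAb sample at the final visit of withdrawn participants. Section 7.2 refers to the schedule for what to collect at discontinuation, but the schedule has no early-discontinuation column.

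The analysis has its own way of handling deviations. The PK-PPS leaves out important deviations affecting PK (Protocol 9.1, SAP 3.5.5). Exclusions are decided through data cleaning and the DEMs (SAP 3.4 and 4.4). The SAP 5.2 listing shows "whether the deviation led to exclusion from the PK-PPS".

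**The concern.** In a multiple-dose trial, withdrawal for a prohibited medicine can at least end exposure to study drug. Here the whole dose has been given on Day 1, and nearly all of the on-study period of the ban comes after it. An exit then removes only the remaining PK, ADAb and safety visits, and with a half-life of about 28 days some of those fall while drug is still present.

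The order of decisions is also wrong. Whether a given medicine or lapse affects PK is a question for the DEM, but the rule ends the profile first. If the DEM decides the deviation was harmless, the missing samples cannot be recovered. The participant then either drops out of the AUC analysis or stays in with a shortened AUC(0-t), because the PK-PPS requires only one derivable parameter and SAP 9.2.1 keeps a participant for whichever parameters can be calculated. AUC and AUC(0-t) are both primary, and bioequivalence requires all three primary parameters to pass.

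**Working it through.** **1. Reproduce the plan's sample size.** Inputs from Protocol 9.9: ratio 0.9, CV 33%, limits 0.80-1.25, 5% one-sided (90% CI), 80% power.

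- Log-scale SD = sqrt(ln(1 + 0.33²)) = 0.3215.
- n per arm = 2 × 0.3215² × (1.645 + 0.842)² / (ln 1.25 − |ln 0.9|)² = 1.278 / 0.1178² = 92.1, rounded up to 93. The stated figure reproduces.
- Exact power of the two one-sided tests at 93 per arm is 80.1%.

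**2. Which CV applies.** Protocol 9.9 gives 21-25% for AUC and 23-33% for Cmax. The 33% is the top of the Cmax range. An exit after the peak leaves Cmax mostly intact and affects AUC and AUC(0-t). Exact power at ratio 0.9:

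| Evaluable per arm | CV 21% | CV 25% | CV 33% |
|---|---|---|---|
| 93 | 98.6% | 94.6% | 80.1% |
| 90 | 98.4% | 94.0% | 78.9% |
| 85 | 97.9% | 92.8% | 76.9% |

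The last column is relevant only if the participant's Cmax is lost as well, through an exit before the peak or exclusion from the PK-PPS.

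**3. How much of the profile is lost.** The half-life of 28 days is from Protocol 4.2. I assume one compartment with first-order absorption and tmax of 4 to 10 days; the documents give neither.

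- ke = ln 2 / 28 = 0.02476 per day. Solving tmax = ln(ka/ke)/(ka − ke) gives ka = 0.932 (tmax 4) and 0.260 (tmax 10).
- Share of AUC observed to time T = [(1 − e^(−ke·T))/ke − (1 − e^(−ka·T))/ka] / (1/ke − 1/ka), with T = study day − 1.

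| Last sample | Share of AUC observed | AUC(0-t) relative to Day 140 | Shortfall |
|---|---|---|---|
| Day 140 | 0.965-0.967 | 1 | – |
| Day 84 | 0.858-0.868 | 0.890-0.898 | 10-11% |
| Day 56 | 0.717-0.737 | 0.743-0.762 | 24-26% |

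After a Day 56 exit, about 26-28% of AUC would be extrapolated, against 3-4% with full sampling. These figures suppose no later sample. An SFU sample taken well after the exit would extend AUC(0-t), but across a long gap bridged by the linear trapezoidal rule.

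**4. Effect on the ratio.** Suppose k more of 93 participants stop at Day 56 in the test arm than in the reference arm, and all stay in the AUC(0-t) analysis. The geometric mean ratio is multiplied by r^(k/93), where r is the relative AUC(0-t) above.

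- Five against none: 0.762^(5/93) = 0.9855 and 0.743^(5/93) = 0.9842, a shift of about -1.5 to -1.6%.
- Three against two (k = 1): about -0.3%.
- Five against five: 0.

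**The case against.** There is a good deal to say for leaving the rule alone.

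- **Frequency.** Treatment of adverse events arising after dosing is exempt, as are paracetamol, oral contraceptives, postmenopausal hormones, supplements and short-term over-the-counter drugs judged free of interaction. Most ordinary post-dose medication would therefore not trigger item 3. This stands, and it is why the event rate is probably low.
- **Force.** The wording is advisory, item 2 rests on Investigator opinion, and the Medical Monitor is to be contacted beforehand where possible. Samples already taken are kept, and the SFU Visit can add one PK and one ADAb sample. This also stands, but one encouraged visit does not replace the missed ones.
- **Item 2.** Staff give the dose, so post-dose noncompliance will often mean missed visits, and a participant who is not attending will yield few samples under any wording. Section 7.3 already requires rescheduling and counselling for missed visits. This stands, and it limits the fix for item 2 to those still willing to attend.
- **Exclusion anyway.** If the medicine does affect PK, the participant leaves the PK-PPS and further samples restore no evaluable profile for the primary analysis. That is correct. The gain is for deviations judged not to matter, and for safety and ADAb follow-up in either case.
- **Truncated profiles.** Short AUC(0-t) values can arise from any dropout, and the DEM may exclude them. A general evaluability rule is a separate matter that this change would not settle.

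A reader might infer that the rule takes power down to 78.9% or 76.9%. The documents do not support that for post-peak exits: those figures use the 33% Cmax CV, while the loss falls on AUC, whose CV is 21-25%.

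**Conclusion.** The point holds as a design weakness of modest size. After Day 1, items 2 and 3 of Section 7.2 end data collection without ending any treatment, and they do so ahead of the review that is meant to decide whether the deviation matters. No section provides for continued PK sampling after such an exit.

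For the individual profile the loss is substantial: about a quarter of AUC(0-t) for an exit at Day 56 and about a tenth at Day 84, under the one-compartment assumption with a 28-day half-life and tmax of 4 to 10 days. For the trial it is probably small. AUC power remains about 93-99% with 85 to 93 evaluable per arm, and a ratio shift of about 1.5% needs all five exits in one arm. Nothing in the documents gives a rate or a reason for imbalance, although the study is open-label and item 2 is a matter of opinion.

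Two stronger readings are tempting. One is that Sections 7.1 and 7.2 contradict each other. They do not: one concerns the drug and the other the study. The other is that the rule threatens the bioequivalence conclusion; the figures above do not show that. The case for a change is that avoidable loss of data can be prevented cheaply. It concerns the post-dose period only, since before dosing the same items can prevent a dose from being given.

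**What to change.** In Protocol Section 7.2, separate the period after dosing for two items. For item 3 (prohibited medication), and for item 2 (noncompliance) where the participant is still willing to attend, record a protocol deviation. Continue the scheduled PK, ADAb and safety sampling to Day 140 with the participant's agreement, and decide PK-PPS inclusion at the DEM.

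Leave the illness, safety, consent, pregnancy, COVID-19 and sponsor or regulatory withdrawal reasons as they are, together with the Investigator's discretion to withdraw a participant for safety. The change concerns data collection and alters no clinical decision.

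The cost is a wording change, a few more visits and a few more profiles to review at the DEM. No analysis in the SAP has to change.

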### **7.3 Lost to follow up**

A study participant will be considered lost to follow up if he or she repeatedly fails to return for scheduled visits and is unable to be contacted by the study site.

The following actions must be taken if a study participant fails to return to the clinic for a required study visit:

- The site must attempt to contact the study participant and reschedule the missed visit as soon as possible and counsel the study participant on the importance of maintaining the assigned visit schedule and ascertain whether or not the study participant wishes to and/or should continue in the study.
- Before a study participant is deemed lost to follow up, the Investigator or designee must make a reasonable effort to regain contact with the study participant (at least 1 phone call and 1 written message to the study participant), and document his/her effort (date and summary of the phone call and copy of the written message in the source documents), to complete the final evaluation. All results of these evaluations and observations, together with a narrative description of the reason(s) for removing the study participant, must be recorded in the source documents. The eCRF must document the primary reason for withdrawal.

Should the study participant continue to be unreachable, he/she will be considered to have withdrawn from the study with a primary reason of lost to follow up documented in the eCRF.

## **8 STUDY ASSESSMENTS AND PROCEDURES**

Study procedures and their timing are summarized in the schedule of activities (Section 1.3).

Protocol waivers or exemptions are not allowed.

Adherence to the study design requirements, including those specified in the schedule of activities (Section 1.3), is essential and required for study conduct.

All screening evaluations must be completed and reviewed to confirm that potential study participants meet all eligibility criteria. The Investigator will maintain a screening log to record details of all study participants screened and to confirm eligibility or record reasons for screening failure, as applicable.

The maximum amount of blood collected from each study participant over the duration of the study, including any extra assessments that may be required, will not exceed 450mL. Repeat or unscheduled samples may be taken for safety reasons or for technical issues with the samples.

## **8.1 Efficacy assessments**

Not applicable.

## **8.2 Safety assessments**

Planned time points for all safety assessments are provided in the schedule of activities (Section 1.3).

### **8.2.1 Physical examination**

Physical examinations will be performed as per Section 1.3. The physical examination will include general appearance; ear, nose, and throat; eyes, hair, and skin; respiratory; cardiovascular; gastrointestinal; musculoskeletal; hepatic; neurological (including limb reflexes); and mental status. Findings considered as clinically significant changes since the physical examination at the Screening Visit will be recorded as AEs.

A full physical examination will be performed at the Screening Visit, Day 3, and SFU Visit. On all other days a physical examination is planned, it will be performed symptom-driven (ie, in case of an AE).

### **8.2.2 Body weight and height**

Body weight will be measured with the study participant wearing no shoes and light clothing (weight should be recorded to one decimal place) according to the schedule of activities in Section 1.3. Height will only be measured at the Screening Visit.

### **8.2.3 Vital signs**

Vital signs (BP [systolic and diastolic], pulse rate, and tympanic body temperature) will be recorded before taking PK samples and with the study participant resting in the supine position for at least 3 minutes in a quiet setting without distractions (eg, television, cell phones).

### **8.2.4 Electrocardiograms**

Single 12-lead ECG will be obtained as outlined in the schedule of activities (see Section 1.3) using an ECG machine that automatically calculates the heart rate and measures PR, QRS, QT, and QTc intervals.

All ECG recordings should be taken before taking PK samples and with the study participant resting in the supine position for at least 3 minutes.

## **8.2.5 Clinical safety laboratory assessments**

See Appendix 2 (Section 10.2) for the list of clinical laboratory tests to be performed and the schedule of activities (Section 1.3) for the timing and frequency.

Laboratory data will be electronically captured by ClinBase, a software tool that ensures quality assurance and enables comprehensive capture of all relevant medical information gathered during the study (Section 10.1.6). The Investigator can assess the data in ClinBase and sign off on them electronically.

All laboratory tests with values considered clinically significantly abnormal during participation in the study should be repeated until the values return to normal or baseline or are no longer considered clinically significant by the Investigator or Medical Monitor. If such values do not return to normal/baseline within a period of time judged reasonable by the Investigator, the etiology should be identified and the Sponsor notified.

All protocol-required laboratory assessments, as defined in Appendix 2 (Section 10.2), must be conducted in accordance with the laboratory manual and the schedule of activities (Section 1.3).

If laboratory values from non-protocol specified laboratory assessments performed at the institution's local laboratory require a change in study participant management or are considered clinically significant by the Investigator (eg, SAE or AE), then the results are to be captured in ClinBase.

## **8.2.6 Tuberculosis test**

Refer to g-q-100573, UCB Tuberculosis Detection Procedure Guideline for details regarding tuberculosis infection status, detection procedures, and the related exclusion criteria.

A QuantiFERON®-TB PLUS GOLD test and a TB questionnaire will be performed at the Screening Visit to identify those study participants who have had TB or may have active or latent TB. Results of this test will be reported as positive, negative, or indeterminate. Study participants with a positive test result will not be included in the study. If the result is reported as indeterminate, then the test can be repeated once. If the repeat test result is reported as indeterminate, then the study participant will not be included in the study.

### **8.2.6.1 Tuberculosis questionnaire**

The questionnaire "Evaluation of signs and symptoms of tuberculosis" should be used as a source document. The questionnaire will be completed at the Screening Visit. The questionnaire will assist with the identification of study participant who may require therapy for TB. A study participant who answers "Yes" to the question "Has the study participant been in close contact with an individual with active TB, or an individual who has recently been treated for TB?" at Screening is excluded. A "Yes" response to any of the other questions within the questionnaire at Screening should trigger further careful assessment to determine if the study participant has latent TB or active TB (see exclusion criterion #6 Section 5.2).

### **8.3 Adverse events and serious adverse events**

The definitions of device-related safety events, (adverse device effects [ADEs] and serious adverse device effects [SADEs]), can be found in Appendix 7. Device deficiencies are addressed in Appendix 7 (Section 10.7).

Adverse events will be reported by the study participant.

The Investigator and any designees are responsible for detecting, documenting, and recording events that meet the definition of an AE or SAE and remain responsible for following up AEs that are serious, considered related to the study treatment or study procedures, or that caused the study participant to discontinue the study (see Section 7).

Confirmed and suspected cases of SARS-CoV-2 infection will be recorded as AEs (or SAE, as required).

#### **8.3.1 Time period and frequency for collecting AE and SAE information**

All AEs and SAEs will be collected from the signing of the ICF and at the time points specified in the schedule of activities (Section 1.3).

In order to ensure complete safety data collection, all AEs occurring during the study (ie, after the signing of the ICF), including any pretreatment and posttreatment periods required by the protocol, must be reported in the CRF even if no study medication was taken but specific study procedures were conducted. This includes all AEs not present prior to the initial visit and all AEs that recurred or worsened after the initial visit.

All SAEs will be recorded and reported to the Sponsor or designee within 24 hours, as indicated in Appendix 4 (Section 10.4). The Investigator will submit any updated SAE data to the Sponsor within 24 hours of it being available.

The Investigator is specifically requested to collect and report to UCB (or its representative) any SAEs (even if the Investigator is certain that they are in no way associated with the IMP), up to 30 days from the end of the study for each study participant, and to also inform study participants of the need to inform the Investigator of any SAE within this period. Serious AEs that the Investigator thinks may be associated with the IMP must be reported to UCB regardless of the time between the event and the end of the study.

The method of recording, evaluating, and assessing causality of AE and SAE and the procedures for completing and transmitting SAE reports are provided in Appendix 3 (Section 10.3).

